To examine the effects of race on acute stress responses to the TSST laboratory stressor the response area under the curve (rAUC) for cortisol will be calculated using trapezoidal approximation with the samples obtained at time zero (T0) to the last measurement (T24m). Analysis will adjust for baseline cortisol levels by subtracting the rectangle defined the baseline sample and total observation time (T24min) from the total area under the curve, thus, it is possible to have negative rAUC values if cortisol levels decline below baseline.⁹¹ A generalized linear regression model will be conducted with rAUC as the dependent variable and race (AA/Black, white) as the between-subjects factor. The effects of nicotine metabolism rates, nicotine dependence, and cigarettes smoked per day will be examined in analysis of covariance that include rAUC as the dependent variable and race as the between-subjects variable. The extent to which cortisol changes are blunted will be determined by calculating the difference between the first and last cortisol assessment during the TSST.⁹⁰ Cortisol values that do not change over time or those that are closer to zero will be considered blunted.³⁰ Similar regression models will be used to test for racial differences in cortisol levels at each timepoint following exposure to an acute laboratory stressor, the proportion who smoke after the TSST, and scores for cigarette craving. A random effect will be added to the statistical models to allow for differences in participants recruited from different sites (MUSC and VCU). Models will be adjusted for known and potential confounders (e.g., nicotine metabolism rates).

Aim 2. Evaluate racial differences in *daily* cortisol patterns between AA/Black and white male smokers. *Hypotheses:* AA/Black smokers will be more likely than white smokers to have blunted daily DCS. Compared to white smokers, AA/Black smokers will have lower absolute cortisol values during the waking day. This aim will examine racial disparities in cortisol responses between AA/Black and white male smokers in their neighborhood and community settings at 4- and 8-weeks after the TSST has been completed. Changes in cortisol levels will be the primary outcome variable and will be measured at multiple critical timepoints during the waking day.

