Sample Size and Power Calculations: A sample size of 50 AA/Black (Mean DCS=0.12, SD=0.15) and 50 white (Mean DCS=0.26, SD=0.30) males achieves 84% power to detect a difference of 0.14 μ g/dL between the 2 groups with a significance level of 0.05 using a two-sided two-sample *t*-test, assuming similar differences between the groups at 4 and at 8 weeks of follow-up. This sample size would also provide 83% power to detect a difference of 0.13 μ g/dL in absolute cortisol value between AA/Black (mean=0.35, SD=0.19) and white (mean=0.48, SD=0.35) males with a significance level of 0.05 using a two-sided two-sample *t*-test.

Statistical Analysis: A similar approach to Specific Aim 1 will be used to examine racial differences in daily cortisol levels. Racial differences in mean cortisol levels at 4 weeks will be modeled by a generalized linear model similar to Specific Aim 1 with the addition of a repeated statement to account for the multiple measures taken for each participant throughout the day and a random intercept to allow for individual differences. The same will be done at 8 weeks post TSST. Models will include race and time-of-day as fixed effects and the interaction between them. Model-based contrasts will be used to conduct group

comparisons based on the fitted model. Blunted cortisol DCS will be defined similarly as in Specific Aim 1. Generalized linear models will be used to examine racial differences in blunted DCS at each post-TSST assessment. Similar models will examine the relationship between blunted DCS (at 4 and 8 weeks post-TSST) and baseline measures of smoking behavior (e.g., smoking history, nicotine dependence, nicotine metabolism rates), and stressors (chronic SES stressors, psychosocial stressors, and structural stressors).

Aim 3: Identify factors that are important to acute and daily stress responses among AA/Black and white male smokers by examining acute and daily cortisol patterns based on exposure to chronic stressors. *Hypotheses:* Acute and daily cortisol responses will be associated with chronic stressors such that men who have greater exposure to SES, structural, and psychosocial stressors will have blunted acute and daily cortisol patterns. The relationship between acute and daily cortisol patterns, nicotine metabolism, and nicotine dependence will also be explored.

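### Aim 2 tests the race difference separately at 4 and 8 weeks, with no contrast over both weeks and no rule for reading two results; a joint model would give one test per outcome and use both collection days

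*Combined protocol and SAP*

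**What the plan says.** All references are to section 10.1, Aim 2, unless stated.

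- **Timing.** The aim is to compare the groups "in their neighborhood and community settings at 4- and 8-weeks after the TSST has been completed".
- **Hypotheses.** There are two, and neither names a week: "AA/Black smokers will be more likely than white smokers to have blunted daily DCS" and "Compared to white smokers, AA/Black smokers will have lower absolute cortisol values during the waking day".
- **Primary outcome.** "Changes in cortisol levels will be the primary outcome variable and will be measured at multiple critical timepoints during the waking day".
- **Power.** The DCS calculation (50 per group; means 0.12 and 0.26; SDs 0.15 and 0.30; 84% power) is made "assuming similar differences between the groups at 4 and at 8 weeks of follow-up". A second calculation, for absolute cortisol (means 0.35 and 0.48; SDs 0.19 and 0.35), states 83%.
- **Mean cortisol analysis.** A model is fitted to the 4-week day with race, time-of-day and their interaction. The repeated statement handles the several samples within a day, and there is a random intercept. Then: "The same will be done at 8 weeks post TSST". Contrasts come from the fitted model, which holds one week.
- **Blunted DCS analysis.** "Generalized linear models will be used to examine racial differences in blunted DCS at each post-TSST assessment".

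There is no week term, no race-by-week term, no combined contrast, no primary week, and no statement of how two results are to be read together.

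**The concern.** Each hypothesis is one statement about race, but the plan answers it with two tests and does not say what counts as support: either week, both weeks, or a particular one. If 4 weeks gives p = 0.03 and 8 weeks gives p = 0.09, the reading is left until after the data are seen.

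There is also a loss of precision. Each man gives four samples on each of two days (section 8.0, Post-Stress Test Saliva Collection), yet each test uses one day. Under the plan's own assumption of similar differences, both days estimate the same quantity, and averaging them is the natural way to estimate it.

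**Working it through.** **Inputs from section 10.1, Aim 2.** 50 per group; two-sided 0.05; two-sample t-test.
- DCS: difference 0.26 − 0.12 = 0.14; SDs 0.15 and 0.30.
- Absolute cortisol: difference 0.48 − 0.35 = 0.13; SDs 0.19 and 0.35.

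**Assumptions not in the documents.** The between-week correlation ρ within a man is not given; 0.2, 0.5, 0.8 and 0.9 are tried. The listed SDs are read as one-visit SDs and taken as equal at both weeks. The true difference is the same at both weeks. Data are complete. Absolute cortisol is treated as one value per visit.

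**Step 1: reproduce the plan's figures for one visit.** SE = √[(SD₁² + SD₂²)/50].
- DCS: √[(0.0225 + 0.0900)/50] = 0.0474; 0.14/0.0474 = 2.95. Power is 82.9% (Welch, 72.1 df) or 83.9% (normal approximation). The stated 84% is therefore about the power of one test at one week.
- Absolute cortisol: √[(0.0361 + 0.1225)/50] = 0.0563; 0.13/0.0563 = 2.31. Power is 62.5% (Welch) or 63.6% (normal). The stated 83% does not follow from these inputs.

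**Step 2: average the two weeks.** The variance of a two-day mean is σ²(1 + ρ)/2, so the SE is multiplied by √[(1 + ρ)/2]. The equivalent one-visit sample size per group is 50 × 2/(1 + ρ). Power is Welch.

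| ρ | SE multiplier | SE reduction | DCS SE | DCS 95% CI half-width (µg/dL) | DCS power | Absolute cortisol power | Equivalent n per group |
|---|---|---|---|---|---|---|---|
| one visit | 1 | – | 0.0474 | 0.095 | 82.9% | 62.5% | 50 |
| 0.2 | √0.60 | 22.5% | 0.0367 | 0.073 | 96.4% | 83.7% | 83 |
| 0.5 | √0.75 | 13.4% | 0.0411 | 0.082 | 92.0% | 74.9% | 67 |
| 0.8 | √0.90 | 5.1% | 0.0450 | 0.090 | 86.6% | 67.1% | 56 |
| 0.9 | √0.95 | 2.5% | 0.0462 | 0.092 | 84.8% | 64.7% | 53 |

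At ρ = 1 the multiplier is 1 and the averaged contrast equals one visit. Under these assumptions it is never worse.

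**Step 3: how often the two tests would split.** With the DCS inputs and identical true differences at both weeks, simulation (100,000 studies per ρ) puts the two Welch tests on opposite sides of 0.05 in about 25%, 20%, 13% and 9% of studies at ρ = 0.2, 0.5, 0.8 and 0.9.

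**Step 4: does a model deliver the formula's precision?** A two-record mixed model for DCS (race, week, race × week, participant intercept; 300 simulated studies each) gave mean model SEs of 0.0366 at ρ = 0.2 and 0.0409 at ρ = 0.5, against 0.0367 and 0.0411 by formula. This check left out site and confounders, and the absolute-cortisol model was not simulated.

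**The case against.** **This is a preference for efficiency, not an error.** The aim names both weeks, so week-specific estimates are a legitimate target, and naming a primary week would settle the reading too. That stands as far as validity goes. But a primary week would leave the second day out of the test, and the documents do neither.

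**The gain rests on an unknown.** This stands. At a correlation of 0.9 the SE falls by only 2.5%. Retention is itself a study aim (Aim 4), and missing days would change the figures.

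**The split rates are sampling noise around 0.05, not truly different weeks.** Correct. They show how often a reading rule would be needed even if the weeks do not differ, and nothing more.

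**A joint model could force one diurnal shape on both weeks.** It would if it held only race × time-of-day and race × week. The separate models let the profile differ by week, so a replacement needs week × time-of-day and the three-way term as well.

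**Stronger readings that the documents do not support:**
- *The weekly analyses are biased or invalid.* They are not. Each is a proper comparison at its own week.
- *False-positive risk is roughly doubled.* It would be about 9.5% per outcome at a correlation of 0.3 and 7.0% at 0.9 if significance at either week counted as support. The plan does not adopt that reading; it simply gives none.
- *The Aim 2 power figures contradict separate weekly testing.* For DCS they do not, since 84% is about one-visit power. The absolute-cortisol mismatch (stated 83%, about 63% from its inputs) is a separate error. It would match a two-week average only at a correlation near 0.25, which the plan does not state.
- *Continuous DCS must replace blunted DCS.* A joint-week analysis works on either scale. Which is primary is a separate question.

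**Conclusion.** The point holds as a recommended improvement. Aim 2 leaves two tests per outcome without a rule for reading them, and each ignores one of two collection days, while the hypotheses are week-free and the DCS power text assumes similar differences. The benefit in precision is moderate if the two days are weakly correlated and small if they are highly correlated; the range in the table is all that can be said without a between-week correlation. It also depends on complete data, equal true differences, and the listed SDs being one-visit SDs. The benefit in clarity, one prespecified 5% test per outcome, does not depend on the correlation.

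**What to change.** **Absolute cortisol.** Fit one mixed model to both weeks with race, week, time-of-day, all two-way interactions and race × week × time-of-day, a participant random intercept and a day-within-participant effect. Keep the site effect and confounder adjustment carried over from Aim 1. Make the race contrast averaged over sampling times and both weeks the single test for this outcome. Report the week-specific contrasts and race × week as secondary.

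**DCS.** Fit one model with two records per man: race, week, race × week and within-man correlation, with the same site and confounder adjustment. Make the week-averaged race contrast the single test, on the scale that the sponsor designates: a mixed model for continuous DCS, or a logistic GEE for blunted DCS (with site as a fixed term, since a GEE has no random effects). Report week-specific results as secondary.

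**Timing.** State this before the cortisol data are examined.

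**Cost.** SAP wording, and one somewhat more complex model per outcome in place of two simple ones. No new data, visits or participants are needed. Week-specific estimates are kept, and the mixed models also retain men who supply only one of the two days. Two outcomes still mean two Aim 2 tests unless one is named primary.

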Aim 1: Examine racial differences in acute physiological stress responses between AA/Black and white male smokers using a laboratory model. The association between acute physiological stress response and tobacco-related behaviors will also be evaluated. *Hypotheses:* AA/Black smokers will be more likely than white smokers to have a blunted cortisol response to an acute laboratory stressor. AA/Black smokers will have lower absolute cortisol values during the acute stressor compared to white smokers. AA/Black smokers will have significantly greater cigarette craving and be more likely to smoke following exposure to an acute physiological stressor compared to white smokers following an acute laboratory stressor.

Sample Size and Power Calculations: This aim will examine racial disparities in cortisol responses to an acute stressor among AA/Black and white male smokers in a laboratory setting. Changes in cortisol levels will be the primary outcome variable and will be measured multiple times during the course of the TSST. A sample size of 50 AA/Black (Mean DCS=0.20, SD=0.20) and 50 white (Mean DCS=0.35, SD=0.30) males achieves 84% power to detect a difference of 0.15 μ g/dL between the 2 groups with a significance level of 0.05 using a two-sided two-sample *t*-test. This sample size would also provide 80% power to detect a difference of 0.14 μ g/dL in absolute cortisol value between AA/Black (mean=0.17, SD=0.19) and white (mean=0.31, SD=0.30) males with a significance level of 0.05 using a two-sided two-sample *t*-test.

Statistical Analysis: First, descriptive statistics will be generated to characterize enrollment outcomes using clinical data (e.g., co-morbidities, age, etc) obtained from the EHR during the recruitment process. Statistical analyses will compare enrollees vs. decliners in terms of race, clinical factors, and smoking history to identify variables that should be controlled for in the analysis of stress reactivity and smoking behaviors.

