Sample Size and Power Calculations: It is hypothesized that men who have a higher nicotine addiction (daily versus non-daily or higher FTND score versus lower) will have higher cortisol levels. A sample size of 100 males achieves 82% power to detect a ratio of 1.25 (25% higher cortisol levels among the highly addicted) when the ratio under the null hypothesis is 1 and the coefficient of variation on the original scale is 0.4 with a significance level of 0.05 using a two-sided two-sample *t*-test.

Statistical Analysis: Similar to Specific Aims 1 and 2, Specific Aim 3 multivariable generalized linear regression models will be used to identify factors that are important to acute (baseline) and daily (4 and 8 weeks post-TSST) stress responses (cortisol patterns). Independent associations between blunted cortisol responses and race, smoking behaviors, nicotine dependence at baseline, SES, and psychosocial and structural stressors will be evaluated.

10.2 Data Storage and Privacy Protection. The data management system for the study will be designed to achieve the major elements of the study including: (1) determination of study eligibility, (2) monitoring recruitment and accrual, (3) generation of study materials, and (4) storage of data from telephone interviews and laboratory assessments. All data collected as part of this study will be stored on a MUSC-based secure password-protected network server. Moreover, access to the server will be monitored by the PI and limited to pertinent study personnel.

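### Aim 2's stated 83% power for daily absolute cortisol comes out at about 63% with the printed SDs; Aim 3's 82% is correct for a CV of 0.4, but that CV is not reconciled with the cortisol variability in Aims 1 and 2

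*Combined protocol and SAP*

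**What the plan says.** All the figures are in Section 10.1, in the Sample Size and Power Calculations paragraphs.

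- **Aim 2, daily absolute cortisol.** "This sample size would also provide 83% power to detect a difference of 0.13" μg/dL "in absolute cortisol value between AA/Black (mean=0.35, SD=0.19) and white (mean=0.48, SD=0.35) males", with 50 men per race and a two-sided test at 0.05.
- **Aim 1, acute absolute cortisol.** 80% power for a difference of 0.14 μg/dL "in absolute cortisol value between AA/Black (mean=0.17, SD=0.19) and white (mean=0.31, SD=0.30) males".
- **Aim 3.** The hypothesis used for power is that "men who have a higher nicotine addiction (daily versus non-daily or higher FTND score versus lower) will have higher cortisol levels". With 100 men, the plan states 82% power for a ratio of 1.25, "when the ratio under the null hypothesis is 1 and the coefficient of variation on the original scale is 0.4", and the test is run "with a significance level of 0.05 using a two-sided two-sample *t*-test". The paragraph does not name the cortisol measurement, give the expected split between addiction groups, or say where 0.4 comes from.
- **Aim 3 analysis.** The models cover acute and daily (4- and 8-week) cortisol responses, and the associations to be estimated are described as "Independent associations between blunted cortisol responses and race, smoking behaviors, nicotine dependence at baseline", followed by SES, psychosocial and structural stressors.

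**The concern.** The Aim 2 statement gives every input its calculation needs, and the stated result does not follow from them. A reader would take the absolute cortisol comparison as well powered, although on the printed SDs more than one true difference of 0.13 in three would be missed.

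The Aim 3 statement is internally consistent, but its variability input is lower than that used for cortisol level elsewhere in the same section. If the Aim 1 and Aim 2 variability carries over, a null nicotine addiction contrast would be much less informative than 82% power suggests.

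**Working it through.** **1. Aims 1 and 2: reproducing the stated powers**

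Inputs: n = 50 per race (Sections 5.0 and 10.1), two-sided 0.05, means and SDs as printed. Standard error SE = √(SD₁²/50 + SD₂²/50); noncentrality = difference/SE. Power is from the unequal-variance t-test, with the normal approximation alongside.

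| Comparison | Difference | SDs | Stated | t | Normal |
|---|---|---|---|---|---|
| Aim 1 DCS | 0.15 | 0.20, 0.30 | 84% | 82.9% | 83.7% |
| Aim 1 absolute | 0.14 | 0.19, 0.30 | 80% | 78.7% | 79.6% |
| Aim 2 DCS | 0.14 | 0.15, 0.30 | 84% | 82.9% | 83.9% |
| **Aim 2 absolute** | **0.13** | **0.19, 0.35** | **83%** | **62.5%** | **63.6%** |

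For the last row: SE = √(0.0361/50 + 0.1225/50) = 0.0563, and 0.13/0.0563 = 2.31. The other three rows have noncentralities of 2.94, 2.79 and 2.95.

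**2. Can anything else explain 83%?**

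- A one-sided test gives 74%, and a log-scale comparison 76%.
- A common SD of 0.19 gives 92%; a common SD of 0.35 gives 45%.
- Averaging weeks 4 and 8 at an assumed between-visit correlation of 0.3 gives about 81%. The same averaging would put Aim 2 DCS at about 95%, against the stated 84%.
- Changing only the AA/Black SD cannot help: with that SD at zero, power is 73% (75% by normal approximation).
- A white SD of 0.25 gives 82.6% (83.3% normal). This value is an assumption and is not in the documents.

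With the printed SDs, 83% power corresponds to a difference of 0.166, or about 0.17, instead of 0.13.

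**3. Aim 3: reproducing the stated 82%**

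Log-scale SD = √ln(1 + CV²) = √ln(1.16) = 0.385. With an assumed 50/50 split, SE = 0.385 × √(2/50) = 0.0771. Noncentrality = ln(1.25)/0.0771 = 0.2231/0.0771 = 2.90. With 98 df, power is 81.8%, so the stated figure reproduces. At the same CV a 40/60 split gives 80%, 30/70 gives 75% and 20/80 gives 63%.

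**4. Aim 3: the CVs implied by Aims 1 and 2**

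CV = SD/mean for absolute cortisol; power is for a ratio of 1.25 at 50/50.

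| Source | CV | Power |
|---|---|---|
| Acute, AA/Black | 0.19/0.17 = 1.12 | 23% |
| Acute, white | 0.30/0.31 = 0.97 | 27% |
| Daily, AA/Black | 0.19/0.35 = 0.54 | 58% |
| Daily, white, printed SD | 0.35/0.48 = 0.73 | 39% |
| Daily, white, SD 0.25 (assumed) | 0.25/0.48 = 0.52 | 62% |

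The addiction groups mix the races, and the stated test is unadjusted. In an even mix, the variance is the mean of the two within-race variances plus a quarter of the squared mean difference.

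- Acute: mean 0.24, SD √(0.06305 + 0.0049) = 0.261, CV 1.09, power 24%.
- Daily: mean 0.415, SD √(0.0793 + 0.0042) = 0.289, CV 0.70, power 42%.

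If race is instead adjusted for, averaging the two within-race log variances gives log SDs of 0.858 (acute) and 0.585 (daily). The ratios detectable with 82% power are then about 1.65 and 1.40. With the assumed white SD of 0.25 the daily ratio is about 1.34.

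**The case against.** For Aim 2 no explanation was found in the documents, so that part stands without qualification.

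On Aim 3 there is a fair case for the plan:

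- **The 82% is not a calculation error.** It follows from its stated inputs at an even split.
- **The comparison figures have no stated source either.** The means and SDs behind the Aim 1 and Aim 2 powers are given without one, and the daily white SD is itself in doubt. The mismatch is a lack of agreement within the plan and does not show which figure is off. Still, with a white SD of 0.25 every implied CV remains above 0.4.
- **The outcome is not named.** The comparison could use an average of several samples, or a covariate-adjusted level, and either would lower the effective CV. To reach 0.4 from the within-race variability, about 80% of the log variance would have to be removed for acute cortisol and 57% for daily cortisol (40% with SD 0.25). That is possible, but the plan does not offer it as the basis for 0.4.
- **The contrast is secondary within Aim 3.** The plan says the relationship of cortisol patterns with nicotine dependence will be explored. Aim 3's main hypothesis concerns chronic stressors and blunted cortisol, which the 82% does not address.

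A reader might infer that 0.4 has been shown to be wrong, or that Aim 3 as a whole is underpowered. The documents support neither reading, for the reasons above.

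**Conclusion.** **Aim 2:** wrong as written. The stated 83% and the printed SDs of 0.19 and 0.35 cannot both be right. If the SDs stand, power is about 63%, an overstatement of about 20 points. A misprinted white SD is plausible, since about 0.25 would restore 83%, but only the sponsor can confirm it.

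**Aim 3:** an unreconciled assumption. The 82% is right for a CV of 0.4 and a near-even split. If the Aim 1 and Aim 2 absolute cortisol figures describe the level being compared, power at 50/50 is 23% to 27% for acute cortisol and 39% to 58% for daily cortisol (printed SDs), or about 24% and 42% with the races mixed. These are conditional scenarios. They bear on the nicotine addiction contrast only, and should not be extended to a null result for Aim 3's chronic stressor hypothesis.

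**What to change.** **Section 10.1, Aim 2.** Check the white SD of 0.35 against its source. If it is right, restate the power as about 63%, or give the difference detectable with 83% power as about 0.17 μg/dL. If it is a misprint, correct the SD and leave the power.

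**Section 10.1, Aim 3.** Name the cortisol outcome behind the ratio and the expected split between addiction groups. Then either show how a CV of 0.4 arises (for example, from the number of samples averaged and their correlation), or restate the power or detectable ratio with the Aim 1 and Aim 2 variability. With within-race variability, 82% power and an even split, that ratio is about 1.65 for acute and 1.40 for daily cortisol, the latter to be updated if the white SD changes. Say that the figure applies to the nicotine addiction contrast.

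**Cost.** One figure corrected and one paragraph rewritten. The stated power may be less favourable. No extra participants or procedures.
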